2.0 Introduction / Background**2.1 Background**

The primary goal of New Health Sciences, Inc. is to improve red cell storage through novel storage methods. Based on our review of the pertinent literature, there is substantial evidence suggesting that prolonged exposure to oxygen during storage results in oxidative damage to the red blood cells leading to decreased therapeutic potential. Therefore, removal of oxygen from red blood cell products prior to storage has potential to preserve the cells in a more physiologically relevant state.

Currently, NHSi has focused on the design and development of a dual compartment bag system designated as the Hemanext Red Blood Cell Processing System. After standard processing of donated whole blood units into leukoreduced packed red blood cells (LR-RBCs) with the appropriate additive solutions, the LR-RBCs would then be placed in the oxygen reduction bag (ORB) which allows for the rapid diffusion of oxygen out of the blood, through a sterile, oxygen-permeable membrane, and into iron-based oxygen sorbents. After processing, the blood is transferred again from the ORB into the Hemanext storage bag (HSB) which will preserve the anaerobic state of the LR-RBC product for the duration of cold storage.

NHSi has conducted preliminary storage tests to ascertain the effects of anaerobic storage on overall blood health in various storage solutions. The research team has focused primarily on percent hemolysis, which is mandated by the FDA to remain below 1% for the duration of storage, as well as ATP and 2,3-DPG levels.

2.2 Product Information**2.2.1 Investigational Product**

The Hemanext Red Blood Cell Processing System is a blood storage device that reduces oxygen and carbon dioxide from leukocyte reduced red blood cells in additive solution. The Hemanext System is an assembly of two disposables, the Oxygen Reduction Bag (ORB) and the Hemanext Storage Bag (HSB). See Figure 1 below for the concept configuration.

Study Protocol

Clinical Investigation to Evaluate the New Health Sciences Hemanext® Oxygen Reduction System for Leukoreduced Red Blood Cells with CP2D Anticoagulant and AS-3 Additive - Pivotal Trial

Protocol #: CLIN-0001

Date: 28 Nov 2017

Page 7 of 65

Figure 1: Investigational Product – Hemanext Processing System Assembly

The ORB consists of the following elements: (a) an inner bag; (b) barrier bag; (c) spacer and (d) quilt of 9 sorbent sachets. The inner bag holds the AS-3 LR RBC and is housed in an outer barrier bag. The barrier bag ensures that there is no ingress of oxygen into the ORB during or post O₂/CO₂ reduction. The inner bag is physically separated from the barrier bag by polyester fabric elements embedded into the outer surface of the inner bag. Materials of construction of the inner bag ensure that oxygen released from the LR RBC is optimally transferred to the surrounding space. The sorbent quilt ensures that oxygen released from the LR RBC is absorbed. The spacer (perforated patterned polyethylene stabilizer) is strategically placed in the space between the inner bag and the sorbent quilt to ensure that all of the surface area of the inner bag is clear and able to transfer oxygen. The oxygen indicator is designed to change color if exposed to oxygen. The ORB has tubing to allow sterile docking of the LR RBC bag. The ORB is connected to the ASB bag via integral tubing. The connections facilitate the transfer of the oxygen reduced LR RBC blood. See Figure 2 below for the concept configuration.

[figure not shown]
Study Protocol

Clinical Investigation to Evaluate the New Health Sciences Hemanext® Oxygen Reduction System for Leukoreduced Red Blood Cells with CP2D Anticoagulant and AS-3 Additive - Pivotal Trial

Protocol #: CLIN-0001

Date: 28 Nov 2017

Page 8 of 65

Figure 2: Investigational Product, ORB components

The HSB consists of the following elements: (a) inner bag; (b) barrier bag; (c) spacer and (d) single sorbent sachet. The materials of construction of the HSB ensure that it is capable of maintaining the appropriate low oxygen environment for additive stored LR RBC in refrigerated environments for 42 days. The inner bag holds the blood and is housed inside the oxygen impermeable barrier bag. A sorbent is strategically placed in the space, between the inner and outer bags, to ensure that low oxygen levels are maintained post reduction by the HSB. See Figure 3 below for the concept configuration.

[figure not shown]
Study Protocol

Clinical Investigation to Evaluate the New Health Sciences Hemanext® Oxygen Reduction System for Leukoreduced Red Blood Cells with CP2D Anticoagulant and AS-3 Additive - Pivotal Trial

Protocol #: CLIN-0001

Date: 28 Nov 2017

Page 9 of 65

Figure 3: Investigational Device, HSB Components

O ₂ Indicator
Barrier Bag
Sorbent Sachet
Spacer
Inner Bag

The LR RBC unit bag is connected using an FDA cleared, sterile docking device to the ORB. The sorbent quilt between the inner bag and the barrier bag creates an O₂/CO₂ starved environment. LR RBC are then transferred by gravity to the ORB inner bag. Once the full unit volume is in the ORB inner bag; the Hemanext system is transferred to a tray on an agitator at room temperature (22+2°C). Its contents are evenly distributed, creating a large thin layer of LR RBC contacting the inner surface of the ORB inner bag. The agitator moves in a side to side motion causing the LR RBC to travel within the inner bag in a wave-like motion at the same rate as the shaker, maintaining a constant agitation of RBC and additive solution. Solution in direct contact with the inner bag surface releases oxygen through the material and into the O₂/CO₂-starved environment between the inner bag and barrier bag of the ORB. Maintaining this agitation of red blood cells and residual plasma\additive solution ensures that oxygen saturated RBCs that are furthest from the walls of the bag exchange oxygen molecules with low oxygenated solution closest to the bag surface, which in turn lose the gained oxygen by constant exposure to the oxygen-starved environment on the outer side of the ORB inner bag. The O₂/CO₂ absorption rate is characteristic of the oxygen reduction container material, exchange surface area, volume of RBC and agitation. At the end of the exposure time of 3 hours, the resulting deoxygenated LR RBC is transferred to the HSB in the kit. The HSB utilizes the same principles as the ORB to preserve a low oxygen and CO₂ environment within its contents. It utilizes a sorbent to maintain this environment and preserve the blood at low O₂ and CO₂.

Study Protocol

Clinical Investigation to Evaluate the New Health Sciences Hemanext® Oxygen Reduction System for Leukoreduced Red Blood Cells with CP2D Anticoagulant and AS-3 Additive - Pivotal Trial

Protocol #: CLIN-0001

Date: 28 Nov 2017

Page 10 of 65

levels for its storage duration of up to 42 days. The HSB is also a transfusion ready device.

Figure 4: Diffusion Mechanism for O₂ Removal

[figure not shown]
[figure not shown]
[figure not shown]

Figure 5: Hemanext Process

STEP 1 – Sterile Transfer LR RBC to ORB

STEP 2 – Agitate in commercial shaker

STEP 3 – Transfer to HSB and store for use

Hemanext Storage Bag (HSB)

Study Protocol

Clinical Investigation to Evaluate the New Health Sciences Hemanext® Oxygen Reduction System for Leukoreduced Red Blood Cells with CP2D Anticoagulant and AS-3 Additive - Pivotal Trial

Protocol #: CLIN-0001

Date: 28 Nov 2017

Page 11 of 65

2.3 Previous clinical experience

Two research studies were conducted to confirm the readiness of the Hemanext RBC processing system for clinical trials in the United States (see table 1 below).

An initial pool and split study was performed with the partnership of Rhode Island Blood Center for donor collection. The storage data was measured internally in NHSI's Blood Lab. Key blood quality metrics (such as ATP and 2,3 DPG) compared favorably for the experimental product to the control product.

After a final product design was reached, a study was conducted independently at the American Red Cross Norfolk lab. The study increased the hold time to 12 hours and was designed to be a pilot of the experimental arm of this protocol. All acceptance criteria were met, and results similar to internal testing were collected. In addition, RBC Morphology was equivalent, it was confirmed that Hemanext may be ATP/DPG rejuvenated at 42 days, and oxygenation dissociation curves matched the DPG profile of Hemanext.

3.0 Purpose / Scope

This trial will serve to generate data sufficient to evaluate the in vitro and in vivo performance of the Hemanext product using Leukoreduced Red Blood Cells generated under conditions of 12-hour room temperature hold.

The objective of this clinical study is to evaluate CP2D/AS-3 leukocyte-reduced RBC stored anaerobically for 42 days after deoxygenation with the Hemanext Storage System. In addition to 24-hour recovery and hemolysis, a list of standard blood quality parameters will be measured.

It is expected, based on these data, that Hemanext processing will maintain physiological levels of these blood quality parameters (such as 2,3 DPG).

4.0 Safety / Regulatory Requirements**4.1 Rationale for Human Use**

The human use portions of this study are whole blood collection, and the measurement of autologous, in vivo, radiolabeled 24-hour red cell recovery and survival of red blood cells stored in AS-3® additive. All other study procedures involve in vitro bench testing only.

While in vitro testing provides an estimate of the in vivo red blood cell recovery and survival, the FDA requires in vivo studies to establish efficacy of a blood storage system; therefore autologous, radiolabeled, in vivo red cell recoveries will be performed in this study.

See section 7.1 for additional information regarding study-associated risks.

Study Protocol

Clinical Investigation to Evaluate the New Health Sciences Hemanext® Oxygen Reduction System for Leukoreduced Red Blood Cells with CP2D Anticoagulant and AS-3 Additive - Pivotal Trial

Protocol #: CLIN-0001

Date: 28 Nov 2017

Page 12 of 65

Table 1: Prior Hemanext™ Studies

Study ID (Year Initiated)	Study Name	Purpose	Number of Subjects	Outcome
RESPR27 (2016)	Hemanext Processing System with 42-day Storage and in-vitro Characterization of Resultant Oxygen Reduced, Leukoreduced, Red Blood Cells in AS-3 vs. Control.	The purpose of this pilot study is to generate data of the current design of the Hemanext Processing System (consisting of an oxygen reduction bag "ORB" and an anaerobic storage bag "HSB", 60" tubing, y-connector and 2 ratchet clamps) and Hemanext process.	20 donors. 10 pools of two donors.	Hemanext O ₂ /CO ₂ reduced RBC meet all in vitro acceptance criteria.
RESPR34 (2017)	12-hour Processing with The Hemanext Red Blood Cell Processing System with 42-day Storage and in-vitro Characterization of Resultant Oxygen Reduced, Leukoreduced, Red Blood Cells in CP2D/AS-3	Confirm the feasibility of the current design of the HEMANEXT RBC PROCESSING SYSTEM and Hemanext process for preparing RCC in 12 hours from blood donation. Obtain P50 values that correspond with DPG levels and rejuvenation data on the post Day-42 stored products to show that Hemanext process does not compromise the ability of Rejuvesol to increase ATP and DPG levels in anticipation of FDA pivotal study.	10 donors	Hemanext met acceptance criteria, P50 tracked 2,3 DPG, and Hemanext demonstrated ability to be ATP/DPG rejuvenated.

4.2 Regulatory Requirements

The clinical investigation shall be conducted according to FDA regulations (21 CFR), as applicable.

Study Protocol

Clinical Investigation to Evaluate the New Health Sciences Hemanext® Oxygen Reduction System for Leukoreduced Red Blood Cells with CP2D Anticoagulant and AS-3 Additive - Pivotal Trial

Protocol #: CLIN-0001

Date: 28 Nov 2017

Page 13 of 65

This study will be conducted under IRB (Institutional Review Board) approvals. All potentially eligible donors will read, have the opportunity to ask questions on, and sign Informed Consent Forms approved by the respective IRB prior to any study related procedures.

5.0 Study Design / Analysis

5.1 Study Design

In vitro and in vivo performance of O₂/CO₂ reduced red blood cells produced with the Hemanext System will be used to demonstrate the acceptability the final product for clearance. To accomplish this, the study will require a total of 100 study donors. The study entails a randomized, paired, 2-x-2 crossover design where every study donor (n = 100) who completes the study will donate a total of two whole blood units with individual units being donated at least 56 days (8 weeks) apart. One unit will be used as the test and the other unit will be used for the control. The order in which the IP and the CP will be used to collect, filter and store the whole blood and appropriate blood products (within the context of the crossover design) will be randomized.

The full clinical investigation is summarized in Table 2. See the study's flow diagram in **Section 13.1** for an additional reference.

Table 2: Hemanext™ Clinical Trial Design Summary

Hemanext Pivotal Clinical Trial Summary	
‘n’ (evaluable) *	93
Pre-filtration storage & filtration conditions	20-24°C
Randomized, Paired, Crossover	Investigational unit filtration <8 hours + up to 4 hours processing
	Control unit filtration < 8 hours
In vivo subgroup study (‘n’)	√ (24-28)
Post-filtration assessments	√
Baseline assessments	√
Post-storage assessments	√

Study Protocol

Clinical Investigation to Evaluate the New Health Sciences Hemanext® Oxygen Reduction System for Leukoreduced Red Blood Cells with CP2D Anticoagulant and AS-3 Additive - Pivotal Trial

Protocol #: CLIN-0001

Date: 28 Nov 2017

Page 14 of 65

5.2 Study Primary Endpoints and Acceptance Criteria

The primary endpoints that will be evaluated in this clinical trial are RBC mass recovery, hemolysis and 24-hour in vivo red cell recovery. The endpoint-associated study acceptance criteria are listed below:

- A one-sided 95% lower confidence limit for the true proportion of packed RBC units with hemolysis at day 42 of < 1% is > 95%.
- The mean 24-hour, post-transfusion, in vivo red cell recovery of at least 75% with a standard deviation of $\leq 9\%$, and the lower limit of a one-sided 95% confidence interval for the population proportion of successes is $\geq 70\%$.
- Red Blood cell recovery $\geq 85\%$; with 95% confidence that at least 95% of units are $\geq 85\%$.

5.3 Donor/Data Criteria**5.3.1 Sample Size**

The sample sizes described within the protocol were selected to demonstrate meeting study primary endpoints that conform to the FDA's 95-95 rule (95% confidence and 95% reliability). For successful endpoint outcomes, the study requires meeting the acceptance criteria in 92 of 93 test units per test condition. Therefore, 93 evaluable study donors will complete the study. In the event of two (2) donors/units with unmet acceptance criterion occurring out of ninety-three (93) evaluable procedures (i.e., within one or more study arm(s) for one or more acceptance criteria/primary endpoints), the study will be discontinued.

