5.4 Statistical Analysis Plan

The data from this study will be analyzed to determine whether the primary endpoints and study acceptance criteria (as recommended by FDA and as listed in section 5.2) were met.

In order to assure that 95% confidence in 95% reliability of the of the lower confidence level of the units meet the acceptance criteria for the primary endpoints, the sample size shall be:

- Ninety-three (93) evaluable procedures in which no more than one (1) failure occurs against the acceptance criteria for the primary endpoints.

Secondary analyses, such as differences in populations by site and comparisons between arms, will be described in more detail within the statistical analysis plan. This formal SAP will be developed in conjunction but separately from this protocol, and filed within the trial master file.

The following, at a minimum, will be presented using descriptive statistics:

- **Donor Disposition:** All data on all study donors enrolled in trial including data identified as evaluable and non-evaluable donations will be presented.
- **Demographics:** Age, gender, weight, height, ethnicity and race will be provided for all study donors enrolled in the trial for both evaluable and non-evaluable donations. A comparison to census data will be performed in the final report.
- **Collection procedure-related data:** Collection duration and ambient temperatures will be provided for both evaluable and non-evaluable donations.

Study Protocol

Clinical Investigation to Evaluate the New Health Sciences Hemanext® Oxygen Reduction System for Leukoreduced Red Blood Cells with CP2D Anticoagulant and AS-3 Additive - Pivotal Trial

Protocol #: CLIN-0001

Date: 28 Nov 2017

Page 20 of 65

- **Filtration & processing procedure-related data:** Temperature, head height, filtration time, filter time, filter weight, and final collection volumes will be provided for evaluable and non-evaluable donations.
- **Laboratory data:** Laboratory data will be provided for evaluable and non-evaluable donations (if applicable). Other than the endpoints detailed in the acceptance criteria, the laboratory data will be presented for information only.
- **Adverse events:** Expected, unexpected and serious adverse events will be reported for all enrolled study donors.

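### The rule of 93 evaluable with at most one failure, and the two-failure discontinuation, are stated for the primary endpoints with no exception for 24-hour in vivo recovery, which they cannot describe

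*Combined protocol and SAP*

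**What the plan says.** Section 5.2 names three primary endpoints. Day-42 hemolysis and RBC mass recovery each carry a 95% confidence, 95% of units criterion. In vivo recovery has a criterion of its own: mean at least 75%, SD at most 9%, and "the lower limit of a one-sided 95% confidence interval for the population proportion of successes is" at least 70%. Table 2 in section 5.1 lists 24-28 donors under "In vivo subgroup study", and Table 3 targets 28.

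Section 5.3.1 says the sample sizes were chosen for "study primary endpoints that conform to the FDA's 95-95 rule", and that "the study requires meeting the acceptance criteria in 92 of 93 test units per test condition". It then sets a discontinuation trigger: two donors or units with an unmet criterion, out of 93 evaluable procedures. A parenthesis explains the scope: "within one or more study arm(s) for one or more acceptance criteria/primary endpoints), the study will be discontinued".

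Section 5.4 says the data will be judged against the criteria "as recommended by FDA and as listed in section 5.2", and gives the sample size as "Ninety-three (93) evaluable procedures in which no more than one (1) failure occurs against the acceptance criteria for the primary endpoints". No section excepts in vivo recovery from either rule.

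**The concern.** A single failure limit is attached to three endpoints, one of which has a much smaller sample and a different criterion. If the limit covers in vivo recovery, two low values among 24-28 donors discontinue a pivotal study whose in vivo data may satisfy every part of section 5.2. If it does not, the text should say so. As drafted, sites and sponsor could reach different decisions from the same data. Section 6.2.13 has sites calculate recovery and report out-of-range values to the sponsor within 24 hours, so the question could arise while the study is running.

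A secondary point is the count itself. The parenthesis could be taken to add up failures over endpoints or arms, so that one hemolysis failure and one RBC recovery failure would stop a study in which each endpoint passes at 92/93.

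**Working it through.** **Inputs.** 93 units and at most one failure (5.3.1, 5.4); 95% confidence and 95% reliability (5.3.1); in vivo n=24-28 (Table 2); in vivo limit of 70% for the proportion of successes (5.2). Limits are one-sided 95% Clopper-Pearson: with f failures in n, the lower limit is the 5th percentile of Beta(n-f, f+1).

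**1. The plan's own figure.** At a true pass rate of 95%, P(at most 1 failure in 93) = 0.95^93 + 93 x 0.05 x 0.95^92 = 0.00848 + 0.04150 = 0.04998, just under 0.05. For n=92 it is 0.05214. So 93 is the smallest n with one failure allowed. The lower limit is 0.95001 at 92/93 and 0.93385 at 91/93. The figure reproduces for each in vitro endpoint taken singly.

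**2. The same standard in vivo.** With zero failures the limit is 0.05^(1/n): 0.8827 at n=24 and 0.8985 at n=28. A 95/95 claim is out of reach at the planned size.

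**3. What the 5.2 proportion part allows.**

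| n | failures | lower limit | at least 70%? |
|---|---|---|---|
| 24 | 2 | 0.7602 | yes |
| 24 | 3 | 0.7077 | yes |
| 24 | 4 | 0.6582 | no |
| 27 | 3 | 0.7373 | yes |
| 27 | 4 | 0.6924 | no |
| 28 | 2 | 0.7918 | yes |
| 28 | 4 | 0.7023 | yes |
| 28 | 5 | 0.6606 | no |

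The allowance is 3 failures at n=24-27 and 4 at n=28. Section 5.2 names no interval method. Wilson allows 3 at n=24-26 and 4 at n=27-28; Wald allows 4 at n=24-27 and 5 at n=28. Under all three, stopping at two is stricter than 5.2.

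**4. Can both happen at once?** Take constructed data with values below either plausible cut-off, 70% or 75%.
- n=24, 22 values of 85% and 2 of 69%: mean 83.7%, SD 4.5%, lower limit 76.0%.
- n=28, 26 values of 85% and 2 of 69%: mean 83.9%, SD 4.2%, lower limit 79.2%.

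Both meet all of 5.2 with two failures.

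**5. How often?** The documents give no failure rate. Over assumed rates per donor (test arm, independent donors, range over n=24-28):

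| assumed failure rate | 5.2 proportion part met | at most one failure |
|---|---|---|
| 0.5% | >99.9% | 99.1-99.4% |
| 2% | 99.8-100% | 89.3-91.7% |
| 5% | 95.6-98.8% | 58.8-66.1% |
| 10% | 71.8-85.8% | 21.5-29.2% |

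The rate turns on the undefined cut-off. If recoveries were Normal with mean 85 and SD 5, P(below 75) = 0.0228 and P(below 70) = 0.00135. The chance of two or more failures with the proportion part still met is then 10.1-13.2% at a 75% cut-off and 0.05-0.07% at 70%.

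**6. Pooled counting in vitro.** For two endpoints in the test arm, assuming independence, compare P(at most 1 of 93) squared (both criteria pass) with P(at most 1 of 186) (not stopped if pooled). The results are 99.2% against 98.5% at a 0.1% failure rate per unit, 84.8% against 76.2% at 0.5%, and 58.0% against 44.4% at 1%. With separate counting there is no gap.

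**The case against.** The strongest reply is that the rule limits itself. Both 5.3.1 and 5.4 count failures out of 93 evaluable procedures, and no in vivo count can be out of 93. Both tie the number to 95/95, which in 5.2 belongs only to hemolysis and RBC recovery. Section 5.4 sends acceptance back to 5.2, and 6.2.13 prescribes only notification of the sponsor for an out-of-range recovery value. Section 5.2 also gives no per-donor in vivo cut-off, so a single donor's failure is not defined. A trigger stricter than the acceptance criterion is not in itself an error.

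Much of this stands. A reader might infer that the plan plainly orders discontinuation at two in vivo failures; the denominator and the missing cut-off do not support a reading that firm. Nor does the text support treating pooled counting as the rule, because 5.3.1 speaks of test units per test condition, which favours a separate count.

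What does not fall away is the other half of the wording. The parenthesis in 5.3.1 names one or more primary endpoints, and 5.4 names the primary endpoints, of which in vivo recovery is one. None of the narrowing phrases states an exception.

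The separate SAP may hold the missing definitions, but it is not part of the text reviewed. Section 5.4 says only: "Secondary analyses, such as differences in populations by site and comparisons between arms, will be described in more detail within the statistical analysis plan". Section 5.3.5.1 also refers to it for reporting partial data sets. Neither says that it settles the scope of this rule.

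**Conclusion.** The point holds as an unresolved scope of a stated decision rule. The figure of 93 with one failure is correct for each in vitro endpoint, and nothing here calls it into question. It cannot apply to in vivo recovery at 24-28 donors, and the text points both ways on whether it is meant to.

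On the wider reading, discontinuation and fulfilment of 5.2 can coincide at two to three in vivo failures (n=24-27) or two to four (n=28), provided the mean and SD conditions also hold. These counts assume Clopper-Pearson and concern only the proportion part. How often this would happen cannot be fixed from the documents: under the assumed Normal(85, 5) it moves from about 10-13% to under 0.1% on the choice of cut-off alone.

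Pooling is a lesser ambiguity. Whether control units count is not stated outright, though the reference to test units suggests that they do not. The matter should be fixed, because it bears on whether a pivotal study stops and the remedy is wording.

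**What to change.** Reconcile 5.2, 5.3.1 and 5.4:
- State that the basis of 93 with at most one failure applies to Day-42 hemolysis and to RBC recovery, each counted separately in test units.
- State that in vivo acceptance is judged by its own criterion in 5.2. Define there an individual success and name the interval method, so that the acceptance number is fixed in advance (with Clopper-Pearson, at most 3 failures at n=24-27 and 4 at n=28).
- The sponsor should state whether the discontinuation trigger covers in vivo values, and whether it is counted per endpoint and per arm.

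The cost is rewording of three sections. No donors or procedures are added.
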